1.3 The Bionic Pancreas in Participants with CFRD

We have obtained IRB and FDA approval for a protocol evaluating the BP in adults with CFRD (IDE G150130/S009) with the previous phone-based configuration of the bionic pancreas. We completed a pilot study of three adult participants with CFRD with the BP in both insulin-only (IOBP) and bihormonal (BHPB) configurations compared to Usual Care (UC) in a three-week, random-order, crossover trial (37). The results of the study are summarized in **Figure 2**. The mean glucose was nominally lower in both the IOBP (149 ± 10 mg/dl) and BHPB arms (139 ± 15 mg/dl) relative to the usual care with insulin pump or multiple daily injection therapy (159 ± 56 mg/dl). During the BHPB arm, all participants achieved a mean

consistent with a hemoglobin A1C under the ADA target, compared to two participants in the IOBP arm and one participant during UC. The % of time <54 mg/dL was low in all three arms (0.2%, 0.5%, and 0.3% respectively) without statistically significant differences between arms for any participant ($p \geq 0.45$) according to time series analysis. No adverse events were reported during the study period. These test participants found the BP easy to use and surveys suggested improved satisfaction and reduced burden of diabetes treatment. Notably, participants rarely announced meals during both BP arms, instead relying on fully automating glycemic control. This provides an example of the reduction in effort that the bionic pancreas may provide. Participants also reported eating more carbohydrates during the BP arms because they felt they could do so while still having good glycemic control. Although this would not be ideal in some patient populations, increased carbohydrate intake combined with adequate insulinization could result in desirable weight gain for CF patients. In addition, one of the participants studied in this pilot study was recently diagnosed with CFRD within the past year and had significant residual beta cell function, as indicated by a low insulin requirement of 0.19 units/kg/day. The fact that the BP worked well for this participant supports the robustness of the dosing algorithm in the setting of significant endogenous insulin production and suggests that it would perform similarly well in patients with lower insulin needs.

[figure not shown]

Figure 2. Outpatient results summarizing the distribution of mean CGM glucose levels and hypoglycemia in the insulin-only BP, bihormonal BP, and usual care comparator arms. Mean CGM glucose levels for each participant in each arm (shown as a black circles) are connected by black lines. For each participant, the circle diameter is proportional to the percentage of CGM glucose values < 54 mg/dL. The heavy circles and heavy red line represent the group means. The horizontal red dashed line refers to the glucose level corresponding to the ADA therapy goal 154 mg/dL (HbA1c $< 7\%$).

1.4 Rationale and Potential Benefits

The experiments to date in human participants with type 1 diabetes have demonstrated the practicality of a wearable automated, bionic pancreas control system for robust glucose regulation using continuous glucose monitoring devices as input to the controller. Given this data in those with type 1 diabetes, we propose to evaluate the bionic pancreas for glycemic control in those with CFRD. We have shown that bionic pancreas is capable of achieving good BG control automatically with minimal hypoglycemia in the face of unrestrained meals and exercise and with trivial patient input (electively announcing meals) in both its insulin-only and bihormonal configurations. Control was particularly good at night, achieving mean BG values in the normal range with almost no hypoglycemia. The studies to date have paved the way for longer-term out-patient studies in a broader population.

The iLet bionic pancreas BG control system was able to provide automatic BG regulation and reduce hypoglycemic episodes. Additionally, the system spares the wearer the relentless tasks of carbohydrate counting, frequent BG monitoring, estimating the effects of specific meals and exercise activity on blood glucose levels, and manual drug administration, which are inexact, demanding, aggravating, and require continuous diligence and vigilance and increases the burden of an already complex management of those with CF. If the bionic pancreas achieves the same degree of glycemic control as those we have seen in

participants with type 1 diabetes, we hypothesize that it may reduce the deleterious complications of CFRD.

The current study is designed to test the capabilities of the insulin-only configuration of the iLet bionic pancreas system in adults with cystic fibrosis related diabetes while they go about their normal daily routines. The primary purpose of this pilot is to assess the feasibility of use in management of CFRD. The logical endpoint in the evolution of exogenous insulin therapy is to treat CFRD with an automated, integrated closed-loop glucose-control system.

2. Hypothesis and Specific Aims

We hypothesize that the wearable iLet bionic pancreas system in the insulin-only configuration can provide superior BG control in participants with CFRD compared to usual care. We hypothesize that glycemic control as measured by CGM time in target range 70-180 mg/dl will be superior with the bionic pancreas compared to usual diabetes care. The specific aims of the study are:

Aim 1. To conduct an outpatient study testing the insulin-only configuration of the iLet bionic pancreas in participants ≥ 10 years of age with cystic fibrosis and CFRD in a random-order crossover study versus usual care.

The study will consist of two 14-day study arms in random order: one using the insulin-only iLet bionic pancreas and one where the participants follow their usual diabetes care. We will include patients who manage their CFRD with either an insulin pump or multiple daily injections of insulin. We will use the default target glucose for the insulin-only iLet, 120 mg/dl, to start. The glucose target may be adjusted upward or downward, which will only be done in consultation with the study staff and based on the participant's glycemic control.

The primary outcome will be the percentage of time in glucose target range, 70 – 180 mg/dl in the last twelve days of each arm. The first two days will be excluded from the primary outcome and analyzed separately to allow for adaptation of the algorithm and washout of any long-acting insulin. The last twelve days are expected to more be predictive of outcomes in long term use.

Aim 2. To document the satisfaction of participants with the iLet bionic pancreas versus usual care. Questionnaires will be administered at the beginning of the study and the end of each arm to gather data on attitudes towards bionic pancreas BG control, quality of life and treatment satisfaction. We hypothesize that treatment satisfaction with the BP will be superior to usual care.

Aim 3. To explore the composition of sputum microbiome in participants with CFRD. We hypothesize that patients with CFRD have a unique microbiome that explains their increase in CF exacerbations. This protocol will serve as an exploratory Aim to provide preliminary data for future studies.

3. Participant Enrollment

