8.2 Outcomes

Study endpoints will be calculated for days 3 – 14 so that any long-acting insulin on board has time to clear and therefore does not affect study outcomes. Adverse events will be reported for the entire study period.

The primary analysis of the designated endpoints will be calculated on an intention-to-treat basis, including data from periods when the bionic pancreas was not in use, if available (Dexcom CGM data may not be available in some failure modes). In cases where an arm was not completed, we will use the available data from that arm in the data analysis. We will calculate percentages, means and standard deviations or medians and interquartile ranges as appropriate. We will use paired t-test for comparison of means for normally distributed data and the Wilcoxon signed rank test for non-normally distributed data. We may, in exploratory analyses, also stratify participants for secondary analyses of the pre-specified endpoints by participant characteristics including: sex, age, use of CGM in usual care, baseline A1c, usual care insulin total daily dose, body mass index, FEV1, CFTR genotype, and/or number of CF exacerbations in the preceding year. Given the potential difference in glucose variability, participants under the age 18 will also be analyzed separately from the adult cohort.

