8.2.3.2 Non-glycemic

- Continuous outcomes:
 - From bionic pancreas:
 - Mean total daily dose (TDD)
 - Mean daily basal insulin dose
 - Mean daily bolus insulin dose
 - Mean daily correction insulin dose
 - Mean daily dose from meal announcements
 - Fraction of time bionic pancreas disconnected by the participant (self-report on daily questionnaire)

- Number of unscheduled infusion set replacements
- Number of unscheduled Dexcom CGM sensor changes
- In the UC arm:
 - Insulin total daily dose (TDD) for participants using an insulin pump or smart pen
 - Mean daily basal insulin dose
 - Mean daily bolus insulin dose
- In both arms:
 - Number of episodes of symptomatic hypoglycemia per 24 hours (reported daily by participants)
 - Amount of carbohydrate taken to treat or prevent hypoglycemia per 24 hours (reported daily by participants)
 - Change in body weight from baseline
 - Questionnaires scores on each questionnaire that is administered

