14.2 Appendix B: Psychosocial questionnaires

Baseline questionnaires are completed by all participants at the Study Start Visit and then after each arm (or within 1 week leading up to each timepoint).

Each questionnaire is described briefly below. Age-appropriate versions of each questionnaire will be administered wherever possible. Parents/guardians of pediatric participants may complete parent versions of these questionnaires where applicable. It is estimated that questionnaires will take less than 1 hour to complete for participants and parents of participants <18 years of age.

Brief Description of Questionnaires

Measure	Construct Measured / Relevant Points	Who Completes / Age Range	Timing of Administration in RCT
Diabetes-Specific Emotional Distress • DDS for ≥ 18 yrs • PAID-C for 10-12 yrs • PAID-T for 13-<18 yrs	Gold standard measures for understanding distress symptoms related to diabetes. • DDS = 28 items • PAID-C = 11 items • PAID-T = 14 items	• DDS: ≥ 18 yrs • PAID-C: 10-12 yrs • PAID-T: 13-<18 yrs	Baseline, after each arm

Measure	Construct Measured / Relevant Points	Who Completes / Age Range	Timing of Administration in RCT
Hypoglycemia Confidence	Includes 8 different common situations where hypoglycemia occurs (e.g., physical activity, driving) and evaluates level of confidence in those situations (9 items)	≥18 yrs	Baseline, after each arm
Diabetes Technology Attitudes	Subjective questions about attitudes related to diabetes technologies and devices (5 items)	≥18 yrs	Baseline, after each arm
INSPIRE Surveys • Adult (Pre & Post) • Youth (Pre & Post)	Measures psychological expectations and response to closed loop treatment. • Adult (Pre, Post) = 22 items • Youth (Pre, Post) = 17 items	• Adult: ≥18 yrs • Youth: 10-18 yrs	All receive Pre-INSPIRE survey at baseline All receive Post-INSPIRE survey after the BP arm ONLY
Fear of Hypoglycemia Scale • Adult Scale • Youth Scale	The HFS measures several dimensions of fear of hypoglycemia among adults with type 1 diabetes. • Adult = Worry (18 items) and behavior (15 items) • Youth = Worry (15 items) and behavior (10 items)	• Adult: ≥18 yrs • Youth: 10-18 yrs	Baseline, after each arm
EQ5D • 5L Version • Y Version	NICE approved QOL measure that translates into economics (5 items)	• 5L Version: ≥18 yrs • Y Version: 10-18 yrs	Baseline, after each arm
WHO-5	5 items	≥10 yrs	Baseline, after each arm
Bionic Pancreas User Opinion Survey	35 items	≥10 yrs	After the BP arm ONLY

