Past Experience with Artificial Pancreas Systems	9 items	≥10 yrs	After the BP arm ONLY

Table 5. Psychosocial Questionnaires for the Person With Diabetes (PWD)

Measure	Construct Measured / Relevant Points	Child Age Ranges	Timing of Administration in RCT
Diabetes-Specific Emotional Distress • P-PAID-C for 10-12 yrs • P-PAID-T for 13-<18 yrs	Gold standard measures for understanding distress symptoms related to diabetes. • P-PAID-C = 16 items • P-PAID-T = 15 items	• P-PAID-C: 10-12 yrs • P-PAID-T: 13-<18 yrs	Baseline, after each arm
INSPIRE Surveys • Parent (Pre & Post)	Measures psychological expectations and response to closed loop treatment. • Parent (Pre & Post) = 21 items	10-<18 yrs	Pre-INSPIRE survey at baseline Post-INSPIRE survey after BP arm ONLY
Fear of Hypoglycemia Scale • Parent Report Scale	The HFS measures several dimensions of fear of hypoglycemia among parents of youth with type 1 diabetes. • Parent = Worry (15 items) and behavior (11 items)	10-<18 yrs	Baseline, after each arm
Bionic Pancreas User Opinion Survey	35 items	All youth (6-<18 yrs)	After BP arm ONLY
Past Experience with Artificial Pancreas Systems	9 items	10-<18 yrs	After BP arm ONLY

Table 6. Psychosocial Questionnaires for Parents of Children Ages 6-<18 Years Old

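### Aim 2 hypothesises superior treatment satisfaction, but no questionnaire given after both arms is described as measuring it

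*Combined protocol and SAP*

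**What the plan says.** Section 2, Aim 2 sets out to document satisfaction with the iLet against usual care. Questionnaires at the beginning of the study and at the end of each arm are "to gather data on attitudes towards bionic pancreas BG control, quality of life and treatment satisfaction". The aim then gives its one hypothesis: "We hypothesize that treatment satisfaction with the BP will be superior to usual care". Satisfaction is listed apart from attitudes and from quality of life, so the plan treats it as a construct of its own.

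Section 7.2 refers the reader to Appendix B for questionnaire detail. Three entries in Table 5 are restricted to the BP arm for their post-treatment assessment: INSPIRE ("All receive Post-INSPIRE survey", underlined as following the BP arm only), the "Bionic Pancreas User Opinion Survey" and "Past Experience with Artificial Pancreas Systems".

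Section 8.2.3.2 lists, under the outcomes for both arms, "Questionnaires scores on each questionnaire that is administered". Section 8.1 refers to a questionnaire on attitudes and expectations at baseline and on day 14 of each arm. For analysis, Section 8.2 says: "We will use paired t-test for comparison of means for normally distributed data and the Wilcoxon signed rank test for non-normally distributed data".

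**The concern.** A superiority hypothesis in a two-arm crossover, tested with the paired methods of Section 8.2, needs the same score from each participant under both treatments. If satisfaction is recorded only after the BP arm, or under no named instrument, there is no usual-care value to pair it with.

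Two consequences follow. Favourable post-BP opinion could be reported as superiority although it has no comparator. Or the measure standing in for satisfaction could be chosen from several questionnaires after the data are seen. Aim 2 is one of three specific aims and, unlike Aim 3, is not labelled exploratory. A usual-care satisfaction score also cannot be collected once that arm has passed.

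**Working it through.** The plan gives no figure to reproduce here. The check sets the Aim 2 promise beside each Table 5 entry.

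| Measure | Construct as described | Ages | Post-treatment timing |
|---|---|---|---|
| DDS / PAID-C / PAID-T | Diabetes distress | 10 and over, by version | Each arm |
| Hypoglycemia Confidence | Confidence in situations where hypoglycemia occurs | 18 and over | Each arm |
| Diabetes Technology Attitudes | Attitudes to technologies and devices | 18 and over | Each arm |
| Fear of Hypoglycemia | Fear of hypoglycemia | 10 and over, by version | Each arm |
| EQ5D | Quality of life | 10 and over, by version | Each arm |
| WHO-5 | None stated | 10 and over | Each arm |
| INSPIRE | Expectations of, and response to, closed loop | 10 and over, by version | BP arm only |
| User Opinion Survey | None stated | 10 and over | BP arm only |
| Past Experience | None stated | 10 and over | BP arm only |

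**Count.** Measures described as treatment satisfaction and given after both arms: 0 of 6 for adults and 0 of 4 for ages 10-17. In the parent battery (Table 6), 2 of 5 measures follow both arms (distress and fear of hypoglycemia), and neither is described as satisfaction.

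**Asymmetry between arms, in items.**
- Adults after usual care: 28 + 9 + 5 + (18 + 15) + 5 + 5 = 85. After BP: 85 + 22 + 35 + 9 = 151.
- Ages 10-12 after usual care: 11 + (15 + 10) + 5 + 5 = 46. After BP: 46 + 17 + 35 + 9 = 107.
- Ages 13-17 after usual care: 14 + (15 + 10) + 5 + 5 = 49. After BP: 49 + 61 = 110.

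The extra 66 adult items and 61 youth items are the three surveys that have no usual-care counterpart.

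**Would the hypothesis be testable with a both-arm scale?** Take a two-sided 5% paired t-test with 80% power. The detectable standardised difference d (mean paired difference divided by its SD) solves power = 0.80 under a noncentral t distribution with n − 1 degrees of freedom and noncentrality d√n:
- n = 20 (adults): d = 0.660
- n = 10 (pediatric maximum): d = 0.996
- n = 30 (all, if one scoring is shared): d = 0.529

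Moderate-to-large differences in adults would be testable at the planned size. What is missing is the measurement, not the participants.

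**Wording elsewhere.** Section 8.1 has expectations collected on day 14 of each arm. Appendix B gives the expectations survey (INSPIRE) at baseline and after the BP arm only. Section 8.2.3.2 places all questionnaire scores under both arms, although three have no post-usual-care score.

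**The case against.** The best reply is that a measure not described as satisfaction may still capture it. Appendix B describes the questionnaires only briefly, some entries carry no construct, and no items are shown. Diabetes Technology Attitudes is given to adults after both arms, and its content might bear on satisfaction with one's devices. The User Opinion Survey might ask participants to rate the BP directly against usual care, and that would address the hypothesis without a separate usual-care score. On this reading the defect is an unnamed endpoint in a pilot aimed at feasibility, where questionnaire scores are among the other outcomes and play no part in sizing the trial for its primary outcome.

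Part of this stands. Item content cannot be seen, so it is not shown that every listed instrument is unsuitable; what is shown is that none is described or designated for the purpose. The Section 8.2.3.2 mismatch is weak, since scores on administered questionnaires can be read as whatever Appendix B schedules in each arm. The Section 8.1 difference is real but small.

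The main point survives. Aim 2 itself separates attitudes from satisfaction, and Technology Attitudes is not given to ages 10-17. If the User Opinion Survey holds comparative items, the plan neither says so nor names them as the endpoint.

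**Conclusion.** The concern holds. Followed as written, the plan produces no designated usual-care satisfaction score, so the single hypothesis of Aim 2 has no measurement assigned to it. This rests on the constructs and timings given in Appendix B and on the absence of a satisfaction endpoint in Sections 8.1 and 8.2.3.2.

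The effect is confined to satisfaction. Distress, fear of hypoglycemia and quality of life can still be compared between arms, as can confidence and technology attitudes in adults. The primary outcome (time in range) and the Section 8.3 sample size are untouched. The plan should be corrected on this point, but the trial's main result does not depend on it.

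**What to change.** **Preferred.** Add one short treatment-satisfaction questionnaire, with age-appropriate versions, at baseline and after both arms, and name its score as the Aim 2 endpoint. Compare arms with the paired t-test or Wilcoxon signed-rank test already in Section 8.2. If adult and youth versions are scored differently, analyse them separately, as Section 8.2 already plans for under-18s.

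**Alternatives.**
- Reword the hypothesis to one named construct already measured after both arms, and state how age-specific versions are handled. For distress, the DDS has 28 items, PAID-C 11 and PAID-T 14, so the adult DDS could be the tested score with youth scores descriptive. Report post-BP opinion descriptively only.
- If the User Opinion Survey does rate the BP against usual care, name those items as the endpoint.

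In every case, align Sections 8.1 and 8.2.3.2 with the Appendix B schedule.

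**Cost.** The preferred option takes a few minutes at three visits already scheduled. Assuming 8 to 10 items, it adds 9.4% to 11.8% to the adult usual-care battery (8/85 to 10/85), 17.4% to 21.7% at ages 10-12 (8/46 to 10/46) and 16.3% to 20.4% at ages 13-17 (8/49 to 10/49). The estimate of under one hour should be rechecked after the BP arm, where adults already answer 151 items. A parent version would add to a battery of 41 or 42 items after usual care (P-PAID 15 or 16, plus 26 for fear of hypoglycemia). The alternatives need wording changes only.

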3.1 Participant Recruitment

Patients will be recruited from the patient population of co-investigator [name], who sees patients in the MGH Cystic Fibrosis clinic, [name] is the CF endocrinologist at the MGH Adult CF Program and the Pediatric program at Boston Children's Hospital and has direct access to patients and resources at both centers. We reviewed the number of patients seen in the MGH CF Center who would be eligible for participation in this study. Of the 196 patients with CF ≥ 18 years old who receive their care at MGH, 45 have CF-related diabetes and have not had a prior lung transplant, suggesting that roughly 45

patients with CF seen at MGH would be eligible for enrollment in the study, not counting patients newly referred to the center (approximately 10 – 15 per year). Removing the exclusion criteria for patients with a history of lung and liver transplant will give us access to an additional 15-20 adults and children with CFRD.

Study recruitment methods may consist of the following:

- IRB approved paper and digital advertisements, brochures, postcards, flyers and/or newsprint advertisements
- Culling of pre-existing databases held by the investigators of patients who have expressed interest in the bionic pancreas.
 - Those identified will be sent one of the aforementioned IRB approved materials via US mail or e-mail, or contacted via phone, and will be provided information about how to complete the consent process.
- Contacting participants enrolled in an approved CFRD Screening Protocol (PHRC IRB # 2020P003149)
- Research Invitations: Patient Gateway Personalized Letters
 - Study staff will review medical records to identify potential participants that meet inclusion and exclusion criteria. Research invitations will be sent electronically using the EPIC Patient Gateway system or via US mail to participants who have not opted out of receiving invitations and meet basic inclusion criteria based on medical record review. These letters will include an opt out period, after which the study team may call participants to gauge their interest in participating if they have not previously indicated they did not wish to be contacted.

All recruitment materials will be approved by the IRB prior to their implementation.

Every attempt will be made to arrange for informed consent to be obtained by an investigator that is not directly involved in the participant's clinical care. If the physician who first discussed the study with the potential participant is their own physician, that physician will be instructed to give the participant the consent form to take home and review and to tell the participant to call back if they wish to participate. Additionally, a different member of the research team that is not involved in the participant's care will contact the potential participant after the investigator has presented the study to them.

Prospective participants will be briefed by a study staff member regarding the study procedures and the inclusion and exclusion criteria. Informed consent will not be obtained at this time. Potential participants will be sent an informed consent document by mail, fax, or e-mail to review prior to their initial consent and screening visit.

